#### **4.3 Pharmacokinetic Analysis**

The PK samples will consist of 2 groups; samples from the PK profile group and samples from all patients of the CetuGEX™-arm before and at the end of each infusion (up to the 10th infusion).

The samples from the PK profile group will be used for noncompartmental analyses. Samples taken from all patients will be described by sampling time point. Further details are given in Section 11.5.

### **5. SAMPLE SIZE DETERMINATION**

Approximately 240 patients will be randomized in this study.

The log-rank test will be used to test the hypothesis that patients assigned to the CetuGEX™ arm have increased PFS compared to patients assigned to the control arm.

The sample size calculation is based on the following assumptions:

- The median PFS in the control arm is expected to be 5.6 months post randomization.
- It is expected that the median PFS in the CetuGEX™ arm can be increased to 8.4 months corresponding to a hazard ratio of 0.67.
- The overall trial duration will be approximately 36 months with an anticipated recruitment time of 24 months, anticipated treatment phase until PFS events are reached of approximately 12 months after randomization of the last patient (data

cut-off for main analysis) and ongoing follow-up for overall survival for at least 24 months after randomization of the last patient.

- Drop-outs are expected to occur at times following an exponential distribution and resulting in a drop-out rate of 10% at the cut-off for PFS analysis.
- Patients will be randomized in a 1:1 ratio.
- The overall two-sided significance level will be 0.05 and the power to be maintained 80%.

Based on these assumptions, approximately 240 patients have to be randomized to observe the required overall number of 192 events.

If the required number of events is not reached as planned after 12 months from last patient randomized, the main analysis will be postponed to obtain more events but not more than additional 6 months.

Assuming a corresponding effect on OS (hazard ratio 0.67) and a median overall survival of 10.6 months in the control group the number of survival events to be observed after a 24-months follow-up for survival will be 183.

## 6. ANALYSIS POPULATIONS

The analysis populations will include the following:

- The intention-to-treat (ITT) population will consist of all randomized patients. The ITT population will be the primary population for the efficacy analysis.
- The safety population (SAF) will include all patients who received at least one dose of trial medication. This population will be used for safety analyses.
- The per-protocol (PP) population will consist of all ITT patients who received at least one dose of trial medication and without major protocol deviations as defined in this SAP and finally decided in a Data Review Meeting before database lock.
- For PK analyses done in all patients the pharmacokinetic (PK) population will consist of all randomized patients who have at least one evaluable post dose concentration. For the PK profile analyses patients in the PK profile group will be included in the PK profile population who had blood samples collected for PK noncompartmental profiling and who had at least one measureable CetuGEX™ antibody concentration.

In the event that a patient is randomized incorrectly or is administered the incorrect study medication, analyses of the ITT population will be based on the assigned treatment whereas all other analyses will be based on the actual treatment.

## **7. GENERAL ISSUES FOR STATISTICAL ANALYSIS**

### **7.1 General Statistical Methodology**

Descriptive summaries will be provided where appropriate for each of the study variables. In general, disposition summaries will be completed for all patients; summaries of protocol violations will be presented for the ITT population. Analyses of demography and baseline variables, and all efficacy analyses will be performed on the ITT and PP population. Safety and exposure analyses will be done on the SAF. All summaries will be presented for each treatment arm and for the total population, unless otherwise specified. Where data are collected over time, both the observed data and the change from baseline will be summarized at each visit.

Continuous variable summaries will include the number of patients with non-missing values (N), mean, standard deviation, median, minimum and maximum, 1st and 3rd quartile.

Categorical variable summaries will include the frequency and percentage of patients who are in the particular category. In general the denominator for the percentage calculation will be based upon the total number of patients in the study population for the treatment arm, unless otherwise specified.

Any patient who does not complete the study per protocol will be included in the analysis with the data available. Response and benefit rates will be based on the observed assessments and the number of patients in the respective population as the denominator, assuming no response/benefit for patients without sufficient data. Other imputation of missing values will not be performed, unless specified in the relevant sections of the SAP.

The last pre-administration observation will be used as the baseline value for calculating post-administration changes from baseline. All data obtained on the eCRF and entered into the database will be provided in separate data listings showing individual patient values.

Free text specifications (“other”) of multiple choice items will be detailed in the listings, in the tables the frequency of “other” will be displayed.

All analysis will be performed using SAS® Software version 9.3 or later.

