- Any Deaths (NCI CTCAE V4.0 Grade 5 TEAEs and/or with an outcome of death)
- NCI CTCAE Grade 4, 3, 2, 1 TEAEs
- Adverse drug reactions (ADRs) (related or possibly related TEAEs)
- TEAEs leading to withdrawal of study treatment

- TEAEs leading to drug interruption or infusion rate reduction
- TEAEs requiring additional medication
- TEAEs constituting IRRs
- TEAEs marked as disease related symptoms

Incidences of TEAEs will be presented for all TEAEs and separately for the combination treatment (TEAE which occurred before first maintenance treatment) and maintenance treatment (TEAE which occurred at or after first maintenance treatment).

Incidences of TEAEs will be calculated on Preferred Term level, on System Organ Class level (SOC) and globally by treatment group. On each analysis level, a patient will be counted only once. Summaries of incidence rates (frequencies and percentages) of individual TEAEs by MedDRA SOC and Preferred Term will be prepared. Such summaries will be displayed for all TEAEs, TEAEs by maximum severity graded according to NCI-CTCAE (Version 4.03), TEAEs by strongest relationship to study treatment, and TEAEs by strongest relationship to chemotherapy. In the SOC/PT tables, events with missing grade or relationship information will be classified into the worst category. No statistical tests will be performed. In addition, separate summaries of incidence rates of IRRs and all TEAEs without IRRs by SOC and PT will be given.

IRRs will be linked to the last infusion administered before the occurrence of the IRR. Incidence rates will be calculated by SOC and PT on a per infusion basis. Moreover the first infusion per patient with a least one IRR will be identified and summarized in frequency tables.

Also, a summary of incidence rates of TEAEs by SOC and PT and of incidence rates of IRRs by FcγRIIIa-allotype subgroups (FF, FV and VV), by FcγRIIa allotypes (HH, HR, RR) the occurrence of ADAs (no/yes) and the CetuGEX™ concentration ( $C_{max}$ ) after the 3rd infusion ( $\leq$  median/ $>$ median) will be prepared.

In the AE listings all recorded AEs will be included, TEAEs will be identified by a flag variable.

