### 10.4 Electrocardiogram

The summary ECG assessment (categories: normal, abnormal – not clinically significant, abnormal – clinically significant) will be tabulated by visit (frequency tables). Additionally, shifts in assessments from baseline to EOS visit will be presented by treatment arm (shift tables).

Descriptive summaries of actual values and changes from baseline will be presented for ECG measures of PR interval, QRS interval, QT interval, QTc interval (Bazett), and HR (heart rate) by visit and treatment arm.

If not available in the clinical database, Bazett's Correction (QTcb) will be derived as follows:

$$\text{Bazett's Correction (QT}_{c_b}\text{)} \quad \text{QT}_{c_b} = \frac{QT_{msec}}{\sqrt{RR}}$$

where: Relative Rate:  $RR = 60 / \text{HR}$   
HR = heart rate obtained from ECG.

Also, the number and percentage of patients in each treatment group with QTc values 451 - 480 ms, 481 - 500 ms or >500 ms and the number and percentage of patients in each treatment group who experienced a change >30 ms or a change >60 ms will be presented by visit.

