### 11.2 Anti-drug Antibodies

The incidence of ADAs will be summarized by sampling time point in frequency tables for the SAF population.

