In addition, for the QLQ-C30 scales, the difference with respect to baseline will be classified as  $\leq -10$ ,  $-10 - 10$ ,  $\geq 10$ . The rates of patients within these ranges will be presented by treatment group and visit. The time from randomization to the first occurrence of a deterioration of at least 10 points ( $\leq -10$  for global and functional scales,  $\geq 10$  for symptom scales) will be analyzed by Kaplan-Meier methods. Patients without occurrence of deterioration will be censored at the last assessment. The estimate of the quartiles of the time to deterioration as well as the associated 95%-confidence intervals will be tabulated by treatment arm together with the p-value of a log rank test.

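### The SAP's default percentage denominator is the whole arm, so by-visit, maintenance-phase and ADA percentages mix retention or sampling with the finding, and the direction of the distortion depends on the category shown

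*SAP*

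**What the plan says.** SAP 7.1 sets the rule for categorical summaries: "the denominator for the percentage calculation will be based upon the total number of patients in the study population for the treatment arm". It is a default, and a closing clause lets other sections override it. The same section also sets the full population for response and benefit rates, on purpose: "the number of patients in the respective population as the denominator, assuming no response/benefit for patients without sufficient data". It then rules out other imputation of missing values unless a section provides for it.

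The following tables fall under the default because their sections name no other denominator:

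- **QTc (SAP 10.4).** The plan is "the number and percentage of patients in each treatment group with QTc values 451 - 480 ms, 481 - 500 ms or >500 ms", and the same for patients "who experienced a change >30 ms or a change >60 ms will be presented by visit".
- **Laboratory, urinalysis and ECOG (SAP 10.2, 10.5).** Frequency tables by visit and arm.
- **QoL change classes (SAP 11.6).** "The rates of patients within these ranges will be presented by treatment group and visit".
- **ADA (SAP 11.2).** "The incidence of ADAs will be summarized by sampling time point in frequency tables for the SAF population". Protocol 13.4.4.1 asks for these tables per treatment arm, and SAP 7.1 presents summaries by arm and in total.
- **Maintenance TEAEs (SAP 10.1).** Incidence is given separately for "maintenance treatment (TEAE which occurred at or after first maintenance treatment". Tables 14.3.1.2.3, 14.3.1.3.3 and 14.3.1.4.3 list the whole safety population.

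SAP 13.2 says that the n shown with summary statistics counts non-missing values. It does not redefine the percentage denominator. The SAP does name another unit where it wants one: IRRs per infusion (10.1) and dose changes per administration (8.4).

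**The concern.** Treatment and scheduled assessments run largely until progression, so the number assessed falls steadily over time. If the denominator stays at the arm total, a by-visit percentage is the product of two things: the rate among patients assessed and the share still assessed. When retention differs between arms, which is what the trial hopes to show, two arms with the same rate among assessed patients print different percentages.

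Late findings are diluted in both arms, by different factors. The QTc outlier tables matter most, because outliers are planned only by visit (Tables 14.3.5.2.5 and 14.3.5.2.6), with no patient-level summary over the whole treatment period. ADA is a separate case: the problem there is who is sampled, not who stays.

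**Working it through.** **The plan's own figure first.** The documents give no number for the denominator issue, so the check is on the planning inputs used below (SAP 5). With medians of 5.6 and 8.4 months the hazard ratio is 5.6/8.4 = 0.667. The Schoenfeld formula, 4 × (1.960 + 0.842)² / (ln 0.667)², gives 191 events, against the stated 192. With the ratio rounded to 0.67 it gives 196. The inputs are consistent.

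**Share still on schedule.** Assume exponential PFS and use PFS as a proxy for time on schedule. Then S(t) = 0.5^(t/median). At an equal true rate r among those assessed, the printed percentage is r × S(t), and the CetuGEX/control ratio is 2^(t × (1/5.6 − 1/8.4)) = 2^(t/16.8), whatever r is. Week 18 is 126/30.4375 = 4.14 months, using the SAP 7.2 conversion.

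| Time | S control | S CetuGEX | Ratio | Adverse, true 10% | Favourable, true 80% |
|---|---|---|---|---|---|
| Week 18 | 0.599 | 0.711 | 1.19 | 6.0% vs 7.1% | 47.9% vs 56.9% |
| 6 months | 0.476 | 0.610 | 1.28 | 4.8% vs 6.1% | 38.1% vs 48.8% |
| 12 months | 0.226 | 0.371 | 1.64 | 2.3% vs 3.7% | 18.1% vs 29.7% |

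The 10% and 80% are illustrative. At 12 months the absolute gap for an adverse finding is r × (0.3715 − 0.2264): 0.7 points for a true 5%, 1.45 for 10%, 2.9 for 20% and 4.4 for 30%. With patients assessed as the denominator, both arms print r at every visit.

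**Which rows apply to which tables.**

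- Laboratory tests and ECG continue every 6 weeks in maintenance, and ECOG is recorded weekly (Protocol 10.1.4). All three rows apply.
- QoL is scheduled to week 18 and then at the Safety Visit (Protocol 10.3.2). Only the 1.19 row applies on treatment.
- ADA is sampled up to Day 1 of Cycle 4 and at the Safety Visit (Protocol 10.3.5.1), in CetuGEX patients only (Protocol 10.1.3; Schedule of Events, note 20). No between-arm ratio arises. If a share p of CetuGEX patients is positive, a total column under 1:1 allocation shows p × 120/240 = p/2.

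**Maintenance TEAEs.** These are not by-visit, so the relevant share is those entering maintenance. Assume entry at week 18 (0.599 vs 0.711) and the same event hazard in both arms, h = 0.05 per month. With λ = ln 2/median (0.1238 and 0.0825 per month), incidence per entrant is h/(h + λ):

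- Per entrant: 28.8% vs 37.7%.
- Per safety-population patient: 0.599 × 28.8% = 17.2% vs 0.711 × 37.7% = 26.8%.

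The ratio falls from 26.8/17.2 = 1.56 to 37.7/28.8 = 1.31. Changing the denominator removes part of the gap. The rest is longer exposure, which a rate per unit of time at risk would remove: the hazards are equal here by construction.

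**The case against.** The strongest reply is that the mechanism is inferred. The rule is only a general default. SAP 7.1 also includes non-completers with the data available and refuses other imputation, and that sits badly with treating departed patients as free of the finding. The table shells are not in the documents, so a missing row or a visible n cannot be excluded. This tempers confidence about the eventual output, but it does not rescue the text: the one denominator rule given is the arm total, and it conflicts with the section's own missing-data rule.

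Four further points on that side stand.

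- A reader might infer that the rule makes CetuGEX look worse throughout. It does not. The same tables carry favourable categories (normal ECG, laboratory values within range, good ECOG, QoL improvement), where the longer-staying arm looks better.
- A reader might carry the 1.64 across every table. The visit schedules confine it to late laboratory, ECG and ECOG visits.
- A reader might conclude that the main toxicity comparisons are compromised. Analyses that do not depend on by-visit attendance are already planned: Kaplan-Meier time to first event for AEs of special interest (SAP 10.1.3), shift to maximum post-baseline CTC grade (Table 14.3.4.1.7), and Kaplan-Meier time to QoL deterioration (SAP 11.6). SAP 10.1 plans no tests on the TEAE incidence tables.
- Incidence per treated patient is a legitimate quantity for maintenance events, and entrants are a post-randomization subset. Neither denominator is free of bias.

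That cetuximab patients would print as 0% for ADA follows from a literal reading of SAP 7.1 with Protocol 13.4.4.1. It is not a known output.

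**Conclusion.** The concern holds in limited form. SAP 7.1 states a rule that, applied literally to by-visit, maintenance-phase and ADA tables, yields percentages that cannot be read as rates of the finding. At equal true rates the longer-staying arm looks worse for adverse categories and better for favourable ones, by about 1.19 at week 18, 1.28 at 6 months and 1.64 at 12 months, with small absolute gaps for uncommon findings.

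These sizes rest on the planning medians, exponential PFS, and PFS as a proxy for time on schedule. Drop-out at an equal rate in both arms would leave the ratios unchanged. If PFS does not differ, both arms are diluted equally and the ratio is 1. The maintenance figures also assume entry at week 18, although patients who stop chemotherapy early enter sooner.

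The effect is largely descriptive. The primary analysis, overall TEAE incidence, best response and maximum-grade shifts are not affected. The point should be corrected, chiefly because the diluted figures are the only QTc outlier percentages planned, but it does not threaten the trial's main conclusion.

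**What to change.** Amend SAP 7.1 and the affected table shells:

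1. **By-visit tables** (laboratory, urinalysis, ECG/QTc, ECOG, QoL classes): the denominator is patients with a non-missing assessment at that visit, with n displayed. For change-from-baseline classes this means a usable change value.
2. **QTc outliers:** add a patient-level row for any post-baseline occurrence.
3. **Maintenance TEAEs** (14.3.1.2.3, 14.3.1.3.3, 14.3.1.4.3): the denominator is safety-population patients with at least one maintenance dose. Add exposure-adjusted rates and a footnote that entrants are a post-randomization subset.
4. **ADA:** the denominator is CetuGEX patients with a sample at that time point, plus an any-post-baseline row. Show no cetuximab or total percentage, since cetuximab patients are not sampled. Record this in SAP 12, because Protocol 13.4.4.1 asks for tables per arm.
5. **Keep** the full-population denominator for overall TEAEs and for response and benefit rates.

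The cost is SAP wording, table shells and some programming. No new data are needed, and the sample size and primary analysis do not change.

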### **7.2 Derived and Computed Variables**

The following derived and computed variables have been initially identified as important for the analysis of the primary and secondary target variables. It is expected that additional variables will be required. The SAP will not be amended for additional variables that are not related to the primary target or key secondary target variables. Any additional derived or computed variables will be identified and documented in the SAS programs that create the analysis files. If the SAP is not amended, further derivations required to support the analyses of primary and secondary target variables will be described in the CSR.

Disease will be evaluated by the investigator (modified irRC) and by independent

centralized reading (modified irRC and RECIST 1.1) and classified as complete response (CR), partial response (PR), stable disease (SD) or progressive disease (PD).

Tumor assessments will be performed by the investigator and independent centralized reading during the combination treatment phase and single-agent maintenance phase based on computed tomography (CT) or magnetic resonance imaging (MRI) of the head and neck region, chest, and abdomen. Subsequent assessments will include head, neck and chest; assessments of the abdomen will only be performed if at baseline metastases were confirmed or if clinical evidence suggests new lesions in these regions. Additional regions might be included if clinically indicated.

Tumor assessments in both study arms will be performed at Screening, every 6 weeks after day of randomization until Week 18 and every 8 weeks thereafter. The tumor evaluation will be performed pre-dose. Results of the assessments performed at Screening will be considered baseline values. The same type of imaging as for baseline assessments should be maintained throughout the study.

For time durations in days that need to be converted to months, the number of days will be divided by factor 30.4375. For time durations in days that need to be converted to years, the number of days will be divided by factor 365.25.

The following table describes the derivation of the primary and secondary efficacy variables related to response and survival in detail.

Response Based Variables			
Computation methods described below will be applied simultaneously to response criteria modified irRC (site, central review) and RECIST (central review)			
Variable Name	Computation Methods, Notes, or Equation(s)		
PFSp  (primary definition)	= Earliest date of progression or death - date of randomization + 1 The earliest date of PD will be used irrespective of PD confirmation		
	Finding	Date of PD of Censoring	Outcome
	No PD or death	Pre and post-baseline imaging done: Date of last imaging	Censored
		No baseline or no post-baseline imaging done: Date of randomization	Censored
	Progression/death documented after a new anticancer treatment has started PD at scheduled visit PD between scheduled visits	Date of last imaging prior to new anticancer treatment Date of imaging Date of imaging	Censored Event Event
PFSs  (sensitivity definition)	= Earliest date of progression or death - date of randomization + 1 The earliest date of PD will be used irrespective of PD confirmation		
	Finding	Date of PD of Censoring	Outcome
	No PD or death	Pre and post-baseline imaging done: Date of last imaging	Censored
		No baseline or no post-baseline imaging done: Date of randomization	Censored
	Progression/death documented after a new anticancer treatment has started PD at scheduled visit PD between scheduled visits*	Date of last imaging prior to new anticancer treatment. Date of imaging Date of next scheduled visit	Censored Event Event
	PD after 2 or more missing scheduled visits	Date of last imaging prior to first missing visit.	Censored
	Death up to 16 weeks (112 days) after last imaging Death later than 16 weeks (112 days) after last imaging	Date of death Date of last imaging	Event Censored
Best overall response	Best modified irRC classification (CR, PR or SD) as assessed by the investigator or by the independent centralized review		

(rates) (BO(R))	SD: follow-up measurements must have met the SD criteria at least once after randomization at a minimum interval of 8 weeks.
Objective response (rate) (OR(R))	Best response of CR or PR
Clinical benefit (rate) (CB(R))	Best response of CR or PR or SD. SD: follow-up measurements must have met the SD criteria at least once after randomization at a minimum interval of 8 weeks
Duration of response	= Date of first progression or death after initial response - date of first response + 1 Date of disease progression is defined as the date of imaging showing disease progression. Date of response is defined as the first date of imaging showing CR or PR. If no progression or death is observed after initial response, the duration of response will be censored at the last date of tumor assessment.
Duration of CR	= Date of first progression or death after initial response - date of first CR + 1 Date of disease progression is defined as the date of imaging showing disease progression. Date of CR is defined as the first date of imaging showing CR. If no progression or death is observed after initial CR, the duration of CR will be censored at the last date of tumor assessment.
Other variables	
Overall survival (OS)	Date of death – date of randomization + 1 If no death is observed, OS will be censored at the last date known to be alive.
Time to treatment failure (TTF)	Date of treatment discontinuation for any reason (including disease progression) as assessed by investigator, treatment toxicity, patient preference, or death) – date of randomization If no treatment discontinuation is observed, TTF will be censored at the date of last study treatment.
Body surface area (BSA)	$BSA [m^2] = \text{SQRT}((\text{weight [kg]} \times \text{height [cm]}/3600))$
Number of combination treatment cycles	Number of treatment cycles with full combination treatment (3 doses of CetuGEX™/cetuximab, one dose of cisplatin/carboplatin, 4 doses of 5-FU) Only cycles in which all planned medication has been given will be counted as a full cycle. Dose reductions will however not prevent a cycle to be counted as full.
Overall treatment duration [weeks]	(Date of last treatment administration – date of first treatment administration) + 1 for CetuGEX™/cetuximab
Treatment duration [weeks] during combination treatment	(Date of last treatment administration within a combination cycle – date of first treatment administration) + 1 for CetuGEX™/cetuximab
Treatment duration [weeks] in maintenance phase	(Date of last treatment administration – date of first treatment administration after last Day 15 administration in combination treatment phase) + 1 for CetuGEX™/cetuximab

Total doses [mg]	Sum of actual doses administered for CetuGEX™/cetuximab cisplatin/carboplatin and 5-FU
------------------	--

\* Scheduled visits are expected to be performed every 6 weeks after day of randomization until Week 18 and every 8 weeks thereafter. An assessment is considered “between scheduled visits” if it is performed more than 7 days before the next scheduled visit.

The following variable will be derived with respect to hospitalization:

Variable Name	Computation Methods, Notes, or Equation(s)
Percentage of days in hospital	(Number of days of hospitalization (sum of all: discharge date [or death date if died in hospital] – admission date +1) divided by number of days from randomization to EOS visit) * 100%

